9.6 Endpoint Analyses

All primary and secondary endpoint data will be presented as descriptive summaries and in subject data listings. Where appropriate, graphical presentations of these summaries will also be provided.

9.6.1 Primary Endpoint Analyses

For the non-inferiority test of SRT sentence scores (Kanso 3 with SCAN 2 FF ON versus Kanso 3 with SCAN 2 (ForwardFocus OFF) in 65 dB SPL SONrearhalf 4TB), the 95% CI (alpha=0.025 one-sided) for the mean paired difference will be estimated. If the upper limit of the 95% CI of the mean paired difference is below 1 dB, the treatment condition is regarded as non-inferior to the control in terms of SRT sentence perception. The non-inferiority margin of 1 dB for SRT is based on clinical consensus.

The primary testing of non-inferiority will be conducted for the PP analysis set. If non-inferiority is demonstrated, the testing will proceed to a test of superiority in the ITT analysis set.

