7.2.7 Randomisation Procedures

Subjects will not be randomised to a treatment condition. To control for order effects, counterbalancing of the test order will be implemented for the primary and secondary speech perception endpoints. All permutations will be represented evenly across the subjects where possible.

SRT SONrearhalf Test order

Primary: Kanso 3 SCAN 2 FF Zoom (Automated ForwardFocus ON) vs Kanso 3 SCAN 2 (ForwardFocus OFF)

Exploratory (2): Kanso 3 SCAN 2 FF Zoom (Automated ForwardFocus ON) vs Kanso 3 SCAN 2 FF Beam (Automated ForwardFocus ON)

Subjects will be tested in the following order:

Subject ID	1st	2nd	3rd
1, 7, 13, 19	SCAN 2 FF Zoom	SCAN 2 FF Beam	SCAN 2 (FF OFF)
2, 8, 14, 20	SCAN 2 (FF OFF)	SCAN 2 FF Zoom	SCAN 2 FF Beam
3, 9, 15	SCAN 2 FF Beam	SCAN 2 (FF OFF)	SCAN 2 FF Zoom
4, 10, 16	SCAN 2 FF Zoom	SCAN 2 (FF OFF)	SCAN 2 FF Beam
5, 11, 17	SCAN 2 FF Beam	SCAN 2 FF Zoom	SCAN 2 (FF OFF)
6, 12, 18	SCAN 2 (FF OFF)	SCAN 2 FF Beam	SCAN 2 FF Zoom

SRT SON3 Test order

Secondary (1): Kanso 3 SCAN 2 FF Zoom (Automated ForwardFocus ON) vs Kanso 3 SCAN 2 (ForwardFocus OFF)

Exploratory (3): Kanso 3 SCAN 2 FF Zoom (Automated ForwardFocus ON) vs Kanso 3 SCAN 2 FF Beam (Automated ForwardFocus ON)

Subjects will be tested in the following order:

Subject ID	1st	2nd	3rd
1, 7, 13, 19	SCAN 2 FF Zoom	SCAN 2 FF Beam	SCAN 2 (FF OFF)
2, 8, 14, 20	SCAN 2 (FF OFF)	SCAN 2 FF Zoom	SCAN 2 FF Beam
3, 9, 15	SCAN 2 FF Beam	SCAN 2 (FF OFF)	SCAN 2 FF Zoom
4, 10, 16	SCAN 2 FF Zoom	SCAN 2 (FF OFF)	SCAN 2 FF Beam
5, 11, 17	SCAN 2 FF Beam	SCAN 2 FF Zoom	SCAN 2 (FF OFF)
6, 12, 18	SCAN 2 (FF OFF)	SCAN 2 FF Beam	SCAN 2 FF Zoom

CNC Words Test Order

Secondary (2): Kanso 3 (CP1170) vs Kanso 2 (CP1150)

Subjects assigned a study ID including ODD numbers (01, 03, 05 etc) will be tested in the following order:

1. Kanso 3
2. Kanso 2

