9.4 Sample Size Determination

This is a non-inferiority study, and the sample size calculation was based on a non-inferiority test for SRT (Speech Recognition Threshold) scores (Kanso 3 Sound Processor with SCAN 2 FF compared to Kanso 3 Sound Processor with SCAN 2 (ForwardFocus OFF) in 65 dB SPL SONrearhalf 4TB).

To reject the null hypothesis of inferior sentence in noise scores (SRT scores), the following parameters were chosen for sample size calculation:

- A non-inferiority margin of 1 dB SRT. This margin is based on clinical consensus. NB: *higher SRT scores represent poorer performance*.

- A standard deviation (SD) of 1.36 dB for the difference (in scores). This SD is calculated from 256 paired differences and is an indicative test re-test SD for both SONrearhalf and SON3.
- A significance level $\alpha = 0.025$ (one-tailed).
- A desired power of 0.8.

Based on these assumptions, a sample size of 17 is required to reject the null hypotheses of inferiority using a confidence interval method (one-tailed 97.5% confidence interval). Allowing for up to 15% attrition, a sample size of 20 subjects is planned for this study.

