9.5 Analysis Populations

This study has a non-inferiority design; therefore, the primary endpoint analysis will be based on the Per Protocol population (PP).

For cases in which the Intent-to-Treat (ITT) and PP populations lead to the same conclusions and interpretations about the treatment effect, the results will be considered to not be influenced by underlying factors such as missing data and protocol deviations, and the results would be considered to be robust and consistent under different analysis populations. A statement to reflect this will be included in the Clinical Investigation Report.

For cases in which the ITT and PP populations lead to different final conclusions or interpretations, the results will be reported for both analysis sets and the differences in outcomes will be identified and explored.

Intent-to-Treat Population

The ITT Population will include all subjects who consented and participated (refer Section 7.2.5).

For the purposes of the analyses of the primary and secondary endpoints, subjects will be included in the analysis regardless of protocol deviations. Missing data will not be imputed. Consequently, only subjects with paired treatment and control measurements will contribute to the analysis.

Per Protocol Population

The PP will include all subjects who have one set of paired measurements from treatment and control (for speech outcomes or SSQ12), without major protocol deviations. Major deviations will be defined at the clean file meeting before database lock. Treatment administration not conducted in the intended counterbalanced order of presentation will also be regarded as a protocol violation. However, it is expected that the sequence and period effects are minimal in this study, if any.

This analysis set will be the primary analysis set for the testing of non-inferiority (primary and secondary hypotheses).

Safety Population

The Safety Population will include all treated subjects. The Safety Population will be used for the safety data analysis.

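### SRT test order is counterbalanced over six sequences, but the planned paired t interval ignores test position: valid and conservative, though it gives up precision that one model term would recover

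*Combined protocol and SAP*

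**What the plan says.** Section 7.2.7 states: "To control for order effects, counterbalancing of the test order will be implemented for the primary and secondary speech perception endpoints". For SONrearhalf, and again for SON3, it sets out all six orders of SCAN 2 FF Zoom, SCAN 2 FF Beam and SCAN 2 (FF OFF), with 4, 4, 3, 3, 3 and 3 of the 20 subjects.

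For the primary endpoint, 9.6.1 says "the 95% CI (alpha=0.025 one-sided) for the mean paired difference will be estimated". Its upper limit is compared with 1 dB in the per-protocol set, and 9.6.2 treats SON3 alike. Section 9.1 makes these intervals t-based. No position, period or sequence term is named, and no sensitivity analysis for order.

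Section 9.5 does address order: "it is expected that the sequence and period effects are minimal in this study, if any". It offers no figure or source. It also counts testing out of the intended order as a protocol violation, does not impute, and uses complete pairs only. Withdrawn subjects are not replaced (7.2.6).

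**The concern.** The design controls test order and the analysis then discards it. A subject's Zoom and OFF runs can be one or two positions apart, in either direction. If scores drift with position, those gaps add spread to the paired differences. Balance cancels the drift in the mean but not in the SD, so the interval is wider than it needs to be. The study is sized at exactly the number that reaches 80% power, so there is little slack. The near-perfect balance also belongs to the full 20 subjects, whereas the plan allows for 15% loss without replacement.

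**Working it through.** **Inputs.** From 9.4: "A non-inferiority margin of 1 dB SRT", an SD of the paired difference of 1.36 dB, one-sided alpha 0.025, power 0.8, 17 evaluable subjects and 20 planned. From 7.2.7: the order table. Two assumptions are not in the documents: a true difference of zero (needed to reproduce 17) and a linear order effect of *e* dB per test position.

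**The plan's own figure.** Paired non-inferiority t-test, non-central t, non-centrality 1/(1.36/√n):
- n = 16: power 78.5%
- n = 17: power 81.2%

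So 17 is reproduced, and 17/0.85 = 20.

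**Position gaps (Zoom minus OFF).**

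| Order | Subjects | Gap |
|---|---|---|
| Zoom, Beam, OFF | 4 | -2 |
| OFF, Zoom, Beam | 4 | +1 |
| Beam, OFF, Zoom | 3 | +1 |
| Zoom, OFF, Beam | 3 | -1 |
| Beam, Zoom, OFF | 3 | -1 |
| OFF, Beam, Zoom | 3 | +2 |

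Sum = -8 + 4 + 3 - 3 - 3 + 6 = -1, so the mean gap is -1/20 = -0.05. Sum of squares = 16 + 4 + 3 + 3 + 3 + 12 = 41, so the mean square is 41/20 = 2.05. With all 20 analysed, the bias at 0.5 dB per position is 0.05 × 0.5 = 0.025 dB.

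**Effect on SD and power.** SD = √(1.36² + 2.05·e²), zero true difference:

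| e (dB per position) | SD (dB) | Plain interval, n = 17 | Plain interval, n = 20 |
|---|---|---|---|
| 0 | 1.36 | 81.2% | 87.7% |
| 0.1 | 1.37 | 80.8% | 87.3% |
| 0.25 | 1.41 | 78.6% | 85.4% |
| 0.5 | 1.54 | 71.2% | 78.8% |

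With position in the model the SD returns to 1.36. Power at n = 17 is then 80.9% with one degree of freedom spent and 80.5% with two, whatever *e* is. Simulation with 3 of 20 lost at random (12,000 runs per setting) agrees. At 0.5 dB per position the mean half-width is 0.78 dB plain and 0.69 dB adjusted, with power of 70% and 81%.

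**Error rate.** In the same simulation at a true difference of 1 dB, the plain interval's one-sided error is 2.6% with no order effect and 1.9% when scores improve by 0.25 dB per position. At 0.5 dB per position it is 1.1% if scores improve and 2.0% if they worsen. With the linear position term it is 2.3-2.6% in these settings.

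**Losing 3 of 20.** Over all 1,140 possible losses, the median absolute mean gap is 2/17 = 0.12. The bias is then 0.12 × 0.25 = 0.03 dB or 0.12 × 0.5 = 0.06 dB. The extremes are (-1 - 6)/17 = -0.41, reached by 1 pattern, and (-1 + 6)/17 = +0.29, reached by 4. At 0.5 dB per position these give 0.21 and 0.15 dB.

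**The case against.** The strongest reply is that the order effect is assumed and the plan already limits it. Section 7.3.2.1 requires a 16-sentence practice run and allows one per condition. Section 7.3.4 keeps all comparisons for an endpoint on one day. An effect of 0.5 dB per position means 1 dB between first and third runs, which equals the whole margin. At 0.1 dB the loss (81.2% to 80.8%) is no larger than the cost of the adjustment. This stands: the benefit depends on an effect nobody has quantified.

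The power loss also shrinks if ForwardFocus helps, as 4.2.2 reports for related devices. At 0.5 dB per position and n = 17, plain-interval power is 88% for an assumed true difference of -0.25 dB and 96.5% for -0.5 dB. The SD may be partly double-counted too: "This SD is calculated from 256 paired differences and is an indicative test re-test SD for both SONrearhalf and SON3", and whether it already contains order variation is not stated. Both points stand.

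A linear term could fit badly if practice affects only the first run. In simulation with a 0.5 dB first-run effect, power was 77% plain, 80% with the linear term and 78% with categorical position, so this carries little weight.

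A reader might infer that ignoring order makes a false claim of non-inferiority more likely, or that dropout seriously biases the result. Neither is supported. The error rate stays at or below nominal, within simulation error, when loss is unrelated to sequence. The typical bias is also a few hundredths of a dB against a 1 dB margin.

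**Conclusion.** The point holds as a matter of efficiency. The planned interval is valid and conservative, but it leaves any order effect in the SD although the design records what is needed to remove it. At n = 17 and zero true difference, the cost is about 0.4 points of power at 0.1 dB per position, 2.6 at 0.25 and 10 at 0.5. It is less if all 20 are analysed, if ForwardFocus helps, or if 1.36 dB already includes order variation.

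The documents do not show that the trial is underpowered, since they give no order effect and expect it to be minimal. That expectation is unsupported by data, and the adjusted model would test it.

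The conclusion is confined to SONrearhalf and SON3; no calculation supports extending it to CNC words. Sections 9.1 and 14.3 refer to a statistical analysis plan. If that plan adds a position term, the point is already met, but nothing in the text reviewed does so.

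**What to change.** In 9.6.1, and in 9.6.2 for SON3, pre-specify a linear model of each subject's paired difference (FF Zoom minus FF OFF) on the difference in actual test position. Take the mean difference as the model's estimate at zero position difference, with its 95% CI, and compare the upper limit with the same 1 dB margin. Keep the plain paired t interval as a sensitivity analysis, and report the position coefficient as a check on the expectation in 9.5. Using the actual position also accommodates subjects tested out of order, who remain in the ITT set used for the superiority step.

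No new data or subjects are needed, only a few lines of text settled before the single primary analysis described in 9.8. The cost is one degree of freedom: 81.2% to about 80.8% power if there is no order effect. Categorical position spends two and costs up to about 2 points in simulation.

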9.6.2 Secondary Endpoint Analyses

As with the primary endpoint, the non-inferiority testing of the secondary endpoints will also be conducted in the PP analysis set. If non-inferiority is demonstrated, the testing will proceed a test of superiority in the IIT analysis set.

For the non-inferiority test of SRT sentence scores (Kanso 3 with SCAN 2 FF ON versus Kanso 3 with SCAN 2 (ForwardFocus OFF) in 65 dB SPL SON3), the 95% CI (alpha=0.025 one-sided) for the mean paired difference will be estimated. If the upper limit of the 95% CI of the mean paired difference is below 1 dB, the treatment condition is regarded as non-inferior to the control in terms of SRT sentence perception. The non-inferiority margin of 1 dB for SRT is based on clinical consensus.

For the non-inferiority test of CNC words in quiet scores (monosyllables), the 95% CI (alpha=0.025 one-sided) for the mean paired difference will be estimated. If the lower limit of the 95% CI of the mean paired difference is above -10%, the treatment condition is regarded as non-inferior to the control in terms of words in quiet perception. The non-inferiority margin of -10% for words in quiet scores (monosyllables) is also based on clinical consensus.

For the non-inferiority test of Global SSQ12 scores, the 95% CI (alpha=0.025 one-sided) for the mean paired difference will be estimated. If the lower limit of the 95% CI of the mean paired difference is above -1, the treatment condition is regarded as non-inferior to the control.

Data from the other questionnaires including the results for individual questions on the SSQ will be summarised descriptively. Qualitative data will be summarised as appropriate.

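### Non-inferiority is decided on the PP set alone, a conflicting ITT result has no stated effect, and PP membership is not fixed before the interim analysis of the primary endpoint

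*Combined protocol and SAP*

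**What the plan says.** Section 9.5 makes PP the primary set for testing non-inferiority, and 9.6.1 repeats it: "The primary testing of non-inferiority will be conducted for the PP analysis set". Section 9.6.2 adds that "the non-inferiority testing of the secondary endpoints will also be conducted in the PP analysis set"; the secondary endpoints with hypotheses are S0N3 sentences, CNC words and Global SSQ12. The condition is declared non-inferior when the 95% confidence limit clears the margin. ITT has a formal test only for superiority, once non-inferiority has been shown.

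Section 9.5 also compares the two sets. If they agree, the report says the result is robust. If they lead to different conclusions, "the results will be reported for both analysis sets and the differences in outcomes will be identified and explored". No sentence says which conclusion then holds.

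On exclusions, 9.5 says "Major deviations will be defined at the clean file meeting before database lock". Departure from the counterbalanced test order is the only specific reason named beforehand. Section 14.3 lists the clean file meeting among the items to be confirmed before lock at the end of the study. Section 9.8 places the first and final analysis of the primary endpoint at the interim, together with the S0N3 endpoint. Investigators are not blinded (7.1.1), and the site is owned and run by the sponsor (7.5).

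**The concern.** With about 20 subjects, one exclusion can move a confidence limit across the margin. The 2.5% error rate of a PP test holds if exclusions are unrelated to outcome. Two things would normally protect that condition: a list of exclusions fixed before results are seen, and a rule saying what happens when ITT fails. The text supplies neither for the primary endpoint. What is at stake is a non-inferiority statement that rests on which one or two subjects were set aside, while the analysis of all paired subjects crosses 1 dB.

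**Working it through.** **Inputs, all from 9.4:** margin 1 dB (higher SRT is worse), SD of the paired difference 1.36 dB, one-sided alpha 0.025, power 0.80, 17 evaluable subjects, 20 planned with 15% attrition. The true mean difference is not stated. I assume 0 for power and 1 dB for the false-claim rate.

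**1. The plan's own figure.** Power = 1 − F(t), where t is the 97.5% point of t on n−1 degrees of freedom and F is the noncentral t distribution with noncentrality (1 − δ)√n / 1.36. At δ = 0 this gives 78.5% for n = 16 and 81.2% for n = 17, so 17 is confirmed. Then 17 / 0.85 = 20, also confirmed.

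**2. The threshold.** Upper limit = mean + t × SD/√n. With n = 20, 2.093 × 1.36/√20 = 0.636, so non-inferiority needs an observed mean below 1 − 0.636 = 0.364 dB.

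**3. Illustration.** Take 20 evenly spaced normal scores with SD 1.36 (limits computed from unrounded values).

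| Observed mean, all 20 | Limit, all 20 | Without worst one | Without worst two |
|---|---|---|---|
| 0.40 dB | 1.036 (fails) | 0.855 (passes) | 0.718 (passes) |
| 0.60 dB | 1.236 (fails) | 1.055 (fails) | 0.918 (passes) |

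In the first row the worst score is 3.08. Removing it moves the mean from 0.40 to (8.00 − 3.08)/19 = 0.259 and also shrinks the SD.

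**4. False-claim rate at a true loss of 1 dB.** 400,000 simulated trials of 20 normal pairs:

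| PP exclusion | PP-only claim |
|---|---|
| none | 2.5% |
| one or two at random | 2.5% |
| the single worst responder | 7.5% |
| the two worst responders | 15.4% |

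If both sets must pass, the rate cannot exceed that of the ITT test, 2.5%, whichever subjects PP drops. This follows because every joint pass is also an ITT pass.

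**5. Cost of requiring both sets.** True difference 0, random exclusions:

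| ITT pairs | Excluded from PP | PP alone | Both sets |
|---|---|---|---|
| 20 | 1 | 85.7% | 84.5% |
| 20 | 2 | 83.6% | 82.2% |
| 20 | 3 | 81.2% | 79.7% |
| 17 | 1 | 78.5% | 76.8% |
| 17 | 2 | 75.4% | 73.4% |

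The loss is 1.2 to 1.5 points with 20 pairs and, allowing for simulation error, 1.7 to 2.1 with 17.

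**6. Timing.** Section 9.5 puts the definition of major deviations at the clean file meeting. Section 14.3 puts that meeting at study conclusion. Section 9.8 puts the only primary analysis before that. No section provides for an earlier clean file meeting or an interim freeze of PP membership. CNC words and SSQ12 are not on the interim list, so this gap concerns the primary endpoint and S0N3.

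**The case against.** Choosing PP as the primary set for non-inferiority, with ITT as a robustness check, is a recognised convention. The plan states it consistently and gives a reason. A conflicting ITT result would have to be reported, so it could not be hidden. A reader might infer that the plan lets PP prevail over ITT. The text does not say so: it leaves the final conclusion open, and that is the defect.

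A reader might also take 7.5% or 15% as this trial's error rate. The documents do not support that. Exclusion needs a major deviation or a wrong test order, not a poor score. Test order is set by subject ID (7.2.7), and all comparisons for an endpoint are completed on one day (7.3.4), which limits deviations driven by outcome. Nor do the documents show that those who judge deviations see the scores. Investigators are unblinded, but no section says who attends the clean file meeting or what is shown there, and 7.5 describes procedures separating investigator and sponsor activities.

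The practical risk for the primary endpoint may be small. At an assumed true benefit of 0.5 dB, ITT with 20 pairs passes in 99.7% of trials. A superiority claim is unaffected, because an ITT upper limit below 0 is also below 1 dB.

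These points reduce the weight of the concern. They do not supply the missing decision rule or remove the timing gap. Most of the exposure comes from the late definition of deviations, so a both-sets rule alone would be an incomplete repair.

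**Conclusion.** The point holds as a gap in the decision rule and in timing. Non-inferiority can be concluded on PP with an ITT limit above the margin and, for the primary endpoint and S0N3, with PP membership not yet fixed when results are produced. The size is a bound: 7.5% or about 15% instead of 2.5%, if the one or two excluded are exactly the worst responders, with normal differences, SD 1.36 dB, 20 pairs and a true loss equal to the margin. Exclusions unrelated to outcome leave 2.5%. Nothing in the documents shows that exclusions will track outcome. Only a claim of non-inferiority without superiority is exposed. No figure can be given for CNC words or SSQ12, because the documents state no SD for them.

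**What to change.** - In 9.6.1 and 9.6.2, state that non-inferiority is concluded only if the 95% confidence limit clears the margin in both the PP and the ITT analysis, and is not concluded if they disagree. Align the paragraph in 9.5 on disagreement between the sets.
- In 9.5 and 9.8, require that major deviations are listed and PP membership is fixed and documented before any outcome data are analysed at the interim. Add a matching interim step to 14.3.
- Keep the superiority step in ITT.

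This needs wording and one earlier membership review, with no new subjects, visits or data. The price of the both-sets rule is the power loss shown above. With 20 ITT pairs and three exclusions, power is 79.7%, essentially the planned 80%. With 17 ITT pairs and any further PP exclusion, power is already below 80% on PP alone, and the rule lowers it by about two more points. Fixing membership early costs no power.

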9.6.2 Secondary Endpoint Analyses

As with the primary endpoint, the non-inferiority testing of the secondary endpoints will also be conducted in the PP analysis set. If non-inferiority is demonstrated, the testing will proceed a test of superiority in the IIT analysis set.

For the non-inferiority test of SRT sentence scores (Kanso 3 with SCAN 2 FF ON versus Kanso 3 with SCAN 2 (ForwardFocus OFF) in 65 dB SPL SON3), the 95% CI (alpha=0.025 one-sided) for the mean paired difference will be estimated. If the upper limit of the 95% CI of the mean paired difference is below 1 dB, the treatment condition is regarded as non-inferior to the control in terms of SRT sentence perception. The non-inferiority margin of 1 dB for SRT is based on clinical consensus.

For the non-inferiority test of CNC words in quiet scores (monosyllables), the 95% CI (alpha=0.025 one-sided) for the mean paired difference will be estimated. If the lower limit of the 95% CI of the mean paired difference is above -10%, the treatment condition is regarded as non-inferior to the control in terms of words in quiet perception. The non-inferiority margin of -10% for words in quiet scores (monosyllables) is also based on clinical consensus.

For the non-inferiority test of Global SSQ12 scores, the 95% CI (alpha=0.025 one-sided) for the mean paired difference will be estimated. If the lower limit of the 95% CI of the mean paired difference is above -1, the treatment condition is regarded as non-inferior to the control.

Data from the other questionnaires including the results for individual questions on the SSQ will be summarised descriptively. Qualitative data will be summarised as appropriate.

